Potential Use of Wisebag in VOICE: For women in the VOICE vaginal groups, use of the Wisebag would provide an objective measure of adherence that does not rely on participant self-report. A benefit of an electronic event-based monitoring system (as opposed to a low-tech, cross-sectional or serial cross-sectional approach such as unannounced product counts through home visits), is that it generates precise and detailed information on date and time of each event, allowing the research team to examine patterns of product use, product "holidays" etc. in addition to overall product adherence level. As described above, the technology was originally designed to serve two functions: a wireless opening-event monitoring system and an adherence intervention tool. The latter function, used in the 2 initial pilot studies from CAPRISA and in Uganda^[11, 15], uses a wireless cell phone technology to send a signal to a server when the bags are opened and send a real-time reminder to participants if events are not recorded within an expected timeframe. Additionally, the online functionality provides daily data on women, even if they forget to bring back their Wisebag at the next study visit. Given the wireless reporting capability of Wisebag, site staff will not be affected. Nevertheless, a simpler, cheaper version of the device is currently being developed for "offline" event monitoring (all opening signal events would be stored on the device's electronic chip and downloaded on a local server at study visits), providing only the assessment component (similar to a MEMS cap) which is the

functionality needed in VOICE. Furthermore, because of the relatively high cost of the current “active device” Wisebag (approximately \$200/bag), the Wisepill company can produce a “dummy” Wisebag which is identical looking, but has no recording system inside the device, in order to provide similar looking bags to all vaginal group women at a VOICE site, while collecting data only on a smaller subset.

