4.2 Summary of Major Endpoints

Primary Endpoints:

- **Technical Performance**
 - Staff-reported and participant-reported technical and user-related problems with device and bag; diary card and signal data from device (“heart beat” and participant-initiated opening-events)
- **Ability to Identify Randomization Arm**
 - Participants’ self-evaluation of their arm assignment and their ability to detect (at study exit) whether a bag is an active or non-active bag
- **Concordance with Self-Report**
 - Opening-event data (downloaded from device at the clinic or sent wireless to server) compared with self-reported diary card and questionnaire data
- **Feasibility and acceptability**
 - Participant attitudes and experiences with Wisebag assessed through questionnaire and open-ended interview data at study exit

Secondary Endpoint:

- Appropriateness of educational materials will be assessed through questionnaire and open-ended interview data at study exit.

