4.4 Time to Complete Accrual

The accrual period is targeted over approximately 8 weeks.

4.5 Study Groups:

The three study groups are as follows:

- "Dummy" or placebo Wisebag group: this group will receive a Wisebag which looks and feels identical to an active-device Wisebag, but has no battery or electronic recording system inside the device.
- "Online device" Wisebag: Active-device Wisebag with wireless component and SIM card for sending in real-time all opening events to a central server, in addition to a battery.
- "Offline device" Wisebag: Active-device Wisebag without the wireless component and the SIM card, and with battery and electronic recording system to store all opening events, which are then downloaded to a server at the clinic site.

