7.5 Blinding Evaluations

At the exit visit, women will be asked by an interviewer if they believe they were assigned to a dummy or an active device Wisebag. Following completion of the behavioral assessments, each participant will be shown two demonstration Wisebags, one dummy and one active, and will ask to indicate to the interviewer which one she believes is the active and which one she believes is the dummy. Data will be recorded on an appropriate CRF.

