10.3 Primary Study Hypotheses

This is primarily an exploratory descriptive study that is not designed to test a hypothesis. However, the objectives of the study are based on the assumption that the "active" Wisebags will successfully and accurately record opening events, and will be acceptable for use by

women in the study, and that women will not be able to distinguish between an active and dummy Wisebag.

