10.5.2 Data Analysis

Performance endpoint

Performance will be assessed by comparing the number of failures (e.g., difficulties downloading stored data or receiving wireless data, battery- or signal-failures) experienced in each of the active-device groups. Questionnaire data reporting participants' user-related problems with the bag, device and/or battery will be tabulated overall and by randomization assignment. As indicated by the distribution of data, count data may be recoded and analyzed as categorical data. Count data will be compared using Poisson regression while categorical data will be compared using Chi-square tests. In cases of skewed data, alternative regression models may be implemented as appropriate.

Ability to Identify Randomization Arm

To assess blinding, the proportion of participants who are able to accurately identify whether they were randomized to the "dummy" or active-device groups will be reported. The proportion of participants who are able to indicate whether a demonstration bag is "dummy" or active (note that offline and online devices are identical, aside from the SIM card inside the online device), upon visual inspection, will also be reported. A summary statistic, such as the Cohen's kappa coefficient, will be used to summarize a) the level of agreement between the participant's response and the true group assignment and b) the level of agreement between the participant's response and the true bag type.

Concordance endpoint

Concordance between signal data and diary data will be summarized for participants assigned to the active device groups, and analysis will include the following: the proportion of participants whose number of events per signal data equals, exceeds, or is lower than the number of events per diary data. No formal testing will be performed on this endpoint.

Feasibility and acceptability endpoint

Feasibility and acceptability data collected at study exit by questionnaires will be summarized overall and by randomization group. No formal testing will be performed on this endpoint. Open-ended interview data will be tabulated, thematically coded and summarized by randomization group.

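### The side-by-side demonstration-bag test is made on sight, so it can support visual indistinguishability only and leaves the protocol's claim about feel unchecked

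*Protocol*

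**What the plan says.** Protocol Section 3.1 makes the success of dummy-versus-active blinding a primary objective. Section 4.2 defines the endpoint as the woman's own view of her assignment together with "their ability to detect (at study exit) whether a bag is an active or non-active bag". Section 10.3 states the working assumption "that women will not be able to distinguish between an active and dummy Wisebag". Neither statement is limited to what can be seen.

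The procedure is in Section 7.5. The woman is first asked which type she believes she had. After the behavioural assessments, "each participant will be shown two demonstration Wisebags, one dummy and one active", and she names which is which. Section 10.5.2 reports the proportion correct with the qualifier "inside the online device), upon visual inspection, will also be reported". It plans a kappa-type statistic for each of the two measures and sets no threshold for success.

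On the bags themselves, Section 2.4 describes a dummy "which is identical looking, but has no recording system inside the device". Section 4.5 goes further and says that it "looks and feels identical to an active-device Wisebag, but has no battery or electronic recording system inside the device".

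**The concern.** The only difference that the protocol describes between dummy and active bags lies inside the device. The one direct comparison of the two types is made by looking, and appearance is the property that the bags are built to share. Section 4.5 also asserts that they feel the same, but neither Section 7.5 nor Section 10.5.2 calls for a woman to pick up, open or close both bags. The measurement is therefore narrower than the endpoint it serves.

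The condition that the blind must survive is also broader than sight. Section 4.1 has women open the bag every day for two weeks. Section 13.5 withholds the blinding objective from participants partly because curious women might open the bag repeatedly to find out whether it is active. The protocol thus treats handling as a route that women might try.

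The result feeds a decision. Section 2.4 envisages similar-looking bags for all vaginal-group women at a VOICE site, with data collected from only a subset. A figure near 50% could be taken as evidence that women cannot tell the bags apart, when the test examined appearance alone.

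**Working it through.** **Plan's own figure.** 50 × (1, 2, 2)/5 = 10, 20, 20, which reproduces Table 3 in Section 10.4. The protocol gives no power, error rate or blinding threshold to reproduce.

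**Passages set side by side.**

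| Item | Section | Limited to sight? |
|---|---|---|
| Endpoint: ability to detect an active bag | 4.2 | No |
| Assumption: women cannot distinguish the bags | 10.3 | No |
| Claim about the dummy: same look and same feel | 4.5 | No |
| Demonstration test: bags are shown | 7.5 | Handling not mentioned |
| Scoring of that test | 10.5.2 | Yes |
| Guess of own assignment | 7.5, 10.5.2 | No; follows two weeks of use of one bag type |

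The fourth and fifth rows are the only side-by-side comparison, and the scoring row confines it to sight.

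**Illustration.** Let d be the share of women who could tell the two bags apart by handling, with the rest guessing. The documents give no value for d, so every value here is an assumption. I also assume that the bags look alike, as the protocol says, and that all 50 women complete the exit visit.

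- Expected proportion correct with handling: p = d + (1 − d)/2 = 0.5 + d/2.
- Each woman labels one bag active and one dummy, so chance agreement is 0.5 and kappa = (p − 0.5)/(1 − 0.5) = 2p − 1 = d.
- On sight only: p = 0.5 and kappa = 0 for every d. For 25 of 50 the exact (Clopper-Pearson) 95% interval is 36% to 64%.

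As a yardstick I use 33 of 50, the smallest count whose one-sided exact binomial tail under guessing is at most 0.025 (it is 0.016). This cut-off is mine; the protocol has none.

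| Assumed d | Expected correct, on sight | Expected correct, handled | Kappa, handled | P(33 or more), on sight | P(33 or more), handled |
|---|---|---|---|---|---|
| 0.2 | 25/50 (50%) | 30/50 (60%) | 0.2 | 0.016 | 0.24 |
| 0.4 | 25/50 (50%) | 35/50 (70%) | 0.4 | 0.016 | 0.78 |
| 0.6 | 25/50 (50%) | 40/50 (80%) | 0.6 | 0.016 | 0.99 |

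**What the own-assignment guess can register.** Suppose a share d = 0.4 could recognise their own bag type from use alone, without a comparison bag, and the rest guess dummy or active with probability 0.5 each.

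- Correct in each arm: 0.4 + 0.6 × 0.5 = 0.7, that is 7 of 10 with a dummy and 28 of 40 with an active bag.
- Share answering dummy: (7 + 12)/50 = 0.38.
- Chance agreement: 0.2 × 0.38 + 0.8 × 0.62 = 0.572.
- Kappa: (0.70 − 0.572)/(1 − 0.572) = 0.30.

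So this measure does respond to handling. However, it responds only to cues that can be recognised without a comparison, and its information on the dummy comes from about 10 women.

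**The case against.** The strongest reply is that no perceptible handling cue is documented. The protocol mentions no difference in weight, balance, sound or response on opening, and its only statement on feel is that the bags match. A missing battery and recorder do not by themselves make a detectable difference. This stands. A reader might infer that women would identify the dummy once they held it, but the documents do not support that. The point is that the test leaves the claim unexamined.

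Second, the own-assignment guess follows two weeks of daily opening and has its own agreement statistic. Holding a single bag is also close to the intended VOICE use, since nothing suggests that a woman there would receive both types. This stands in part: handling is covered, but without a comparison bag and with only about 10 dummy holders.

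Third, being shown a bag does not rule out touching it, and Section 7 leaves detailed instructions to a study-specific procedures manual that is not at hand. That is fair for Section 7.5 taken alone. Section 10.5.2, however, names sight as the basis of the reported result. The phrase could conceivably mean external examination without opening the device casing; if so, the wording needs clarifying.

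Fourth, the figures for d are invented, and at d = 0.2 even a handled test would usually fall short of 33 of 50. Both statements are true. The table shows what the test could register, not what is likely.

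Finally, a reader might infer that the test is biased towards declaring success, or that dummies would go to most women at a VOICE site. Neither is supported. The study is descriptive, sets no threshold, and labels this result as visual. Section 2.4 confines the bags to vaginal-group women, which is 2 of the 5 equal arms in Section 2.2 (40%), and only some of those women would hold a dummy.

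**Conclusion.** The point holds as a mismatch between a primary endpoint and how one of its two measures is taken. Detection is defined without restriction to sight, the dummy is described as differing only internally, and the side-by-side test is reported on sight. A chance-level result would therefore show that the bags look alike and would say nothing about whether they feel alike.

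The size cannot be estimated from the documents. If the bags look alike, the sight-only test expects 50% correct and kappa 0 for any d, while a handled test would expect 60% to 80% for d between 0.2 and 0.6. These values rest on an assumed d and on all 50 women completing; Section 7.2 allows for loss to follow-up. If the bags do feel the same, d is 0 and both tests give the same answer. No error rate is affected. What is at stake is how a primary result is read when dummy use among VOICE vaginal-group women is considered. The change is worth making because it is cheap.

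**What to change.** In Section 7.5, have each woman state her choice on sight, then pick up, open and close both demonstration bags and state her choice again. Record both answers on the CRF.

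In Section 10.5.2, replace the sight-only qualifier with wording such as *on sight and after handling*. Report the proportion correct and the kappa for each of the two answers, and describe any sight-only result as visual indistinguishability only.

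The cost is about one extra minute and one CRF line per exit visit, with no new devices or staff. The blinding result may turn out less favourable than one based on sight alone.

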2.6 Study Hypotheses and Rationale for Study Design

2.6.1 Study Hypothesis

This is primarily an exploratory descriptive study that is not designed to test a hypothesis. However, the objectives of the study are based on the assumption that the “active” Wisebags will successfully and accurately record opening events, and will be acceptable for use by women in the study, and that women will not be able to distinguish between an active and dummy Wisebag.

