4 STUDY DESIGN

4.1 Identification of Study Design

MTN-003-P01 is a three-arm, randomized, placebo-controlled, double-blinded pilot study of Wisebag for monitoring daily product use. The study is double-blinded with respect to participants and investigators, (but not for pharmacy and information technology (IT) staff who will manage the download of the electronic data and the battery charging of Wisebag devices). Approximately 50 participants will be randomized to the 3 study arms in a 1:2:2 ratio. The 3 groups will be “dummy” Wisebag (n~10) “Online device” Wisebag (n~20), or “Offline device” Wisebag (n~20).

There will be two study visits: an enrollment visit and one follow-up/exit visit, two weeks after enrollment. During study participation, participants will be asked to open their assigned Wisebag at approximately the same specified time daily, to peel off one sticker from a set of study stickers inside the bag, and place the sticker on the appropriate day of the week on a study provided diary card. After two weeks of daily openings, participants will be asked to return to the study clinic for an exit visit with their Wisebag and diary card.

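### The demonstration-bag test is summarised only as correct labelling, which cannot by itself show that women cannot tell the dummy and active bags apart

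*Protocol*

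**What the plan says.** The second primary objective is to assess whether blinding of the dummy against the active bag succeeded (Protocol 3.1). The assumption behind it, in 2.6.1 and again in 10.3, is "that women will not be able to distinguish between an active and dummy Wisebag". The endpoint in 4.2 is worded more narrowly, as "their ability to detect (at study exit) whether a bag is an active or non-active bag".

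Section 7.5 collects two answers at exit. The woman first says whether she believes her own bag was a dummy or active. Then, after the behavioral assessments, "each participant will be shown two demonstration Wisebags, one dummy and one active", and she states "which one she believes is the active and which one she believes is the dummy".

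Section 10.5.2 reports the share of women who identify the demonstration bag type, and proposes a summary such as Cohen's kappa for "the level of agreement between the participant's response and the true bag type". Own-assignment guesses are summarised in the same way, but separately. The text does not link the two answers. It sets no success threshold, and the study is described as exploratory.

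**The concern.** Telling two bags apart and naming them correctly are different abilities. The planned summaries record only naming. A woman who clearly sees a difference but attaches the labels the wrong way round is scored exactly like a woman who guessed wrong. If women who see the difference disagree about which bag is active, their right and wrong labels cancel and the result looks like guessing.

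This matters because of the dummy's purpose. Under Protocol 2.4 it is meant to look identical, so that all vaginal-group women at a VOICE site carry similar bags while data come from only a subset. Section 4.5 says the dummy looks and feels the same as an active bag. If women can sort the bags into two kinds, that purpose is weakened even when they do not know which kind records. Section 2.4 also names blinded use of the dummy among the features tested to inform scale-up. A chance-level label score read as evidence of indistinguishable bags would be weak support for that step.

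**Working it through.** **Inputs from the protocol.** "Approximately 50 participants will be randomized to the 3 study arms in a 1:2:2 ratio" (4.1), so 10 dummy, 20 online and 20 offline: 40 active (80%) and 10 dummy (20%). The test is a two-bag choice, so a woman is right on both bags or wrong on both, and chance is 50%. The protocol gives no kappa, threshold or power for this test, so there is no stated figure to reproduce.

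**Assumptions, not in the documents.** All 50 women complete the test. A woman who sees the difference labels the bag of her own type as she labelled her own bag. A share q believe their own bag is active, with the same q in both arms. Women who see no difference guess.

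**Kappa.** Over 100 bag ratings, half active and half dummy, expected agreement is 0.5. With proportion correct p, kappa = (p - 0.5)/(1 - 0.5) = 2p - 1.

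**Planned score when every woman sees the difference.** An active-arm woman is right if she believes her bag is active (probability q). A dummy-arm woman is right if she believes hers is a dummy (probability 1 - q). So p = 0.8q + 0.2(1 - q).

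| q | active arm correct | dummy arm correct | pooled p | kappa |
|---|---|---|---|---|
| 0.2 | 20% | 80% | 32% | -0.36 |
| 0.35 | 35% | 65% | 41% | -0.18 |
| 0.5 | 50% | 50% | 50% | 0 |
| 0.65 | 65% | 35% | 59% | 0.18 |
| 0.8 | 80% | 20% | 68% | 0.36 |
| 1 | 100% | 0% | 80% | 0.6 |

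If no woman sees a difference, p = 50% and kappa = 0, the same as the q = 0.5 row.

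**Where the score misleads.** An exact two-sided test of 50% with n = 50 rejects at 17 or fewer, or 33 or more, correct (actual level 0.033). At q = 0.2 and q = 0.8 the expected counts are 16 and 34, each with p-value 0.015, so the planned score would show a departure from chance. The expected count 50 × (0.2 + 0.6q) stays within 18 to 32 for q from (0.36 - 0.2)/0.6 = 0.27 to (0.64 - 0.2)/0.6 = 0.73.

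**A complementary score.** Take the proportion of women who give the demonstration bag of their own true type the label they gave their own bag. If a share d see the difference and label by their own bag, its expectation is d + 0.5(1 - d): 50% at d = 0, 75% at d = 0.5 and 100% at d = 1, for every q. The same exact region has power 0.945 at 75%.

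**Where the complementary score fails.** Suppose every woman names the pair correctly from a visible cue, having earlier guessed her own assignment. The planned score is 100% and kappa is 1. The complementary score is then 0.8q + 0.2(1 - q): 41%, 50% and 59% at q = 0.35, 0.5 and 0.65. Each score can miss what the other detects.

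**Where both fail.** If every woman sees the difference but her label is a coin flip unrelated to her belief about her own bag, both scores have expectation 50%. Chance-level results on both are therefore necessary for calling the bags indistinguishable, but they are not proof.

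**The case against.** The strongest reply is that the score matches its endpoint. Section 4.2 defines detection as saying whether a bag is active or not, which is naming, and 10.5.2 scores naming. That stands: the label score is a fair measure of the endpoint as worded and should be kept. The gap is only against the broader assumption in 2.6.1 and 10.3.

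Second, nothing in the documents says women label by reference to their own bag, or gives any value of q. That also stands, and it limits the size of the point. If all discriminating women shared the same wrong label, kappa would be -1 and would expose the difference.

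Third, the choice of statistic is left open, and an analysis plan not shown could add a further summary. That is true of the statistic, but 10.5.2 fixes its target as agreement with true bag type, and a different statistic with the same target has the same blind spot.

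A reader might infer three stronger things. One is that the planned analysis is wrong for its endpoint; 4.2 does not support that. Another is that a chance-level score would send dummy bags into VOICE; the protocol sets no such rule, own-assignment guesses are a separate blinding measure, and exit interviews are also analysed. The third is that the complementary score should replace the label score as the criterion. That is unsound because the own-bag answer is taken before the pair is shown, so the new score can sit at 50% when all 50 women name the pair correctly.

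**Conclusion.** The point holds as a limit on interpretation. Correct labelling alone cannot establish that the bags are indistinguishable: a proportion correct of 50% with kappa 0 is compatible with no woman seeing a difference and with every woman seeing one. The misleading result requires that women who see a difference split in how they name it. Under own-bag labelling that means q around 0.5, with the expected count inside the chance band for q of roughly 0.27 to 0.73; outside that range the planned score departs from chance. Own-bag labelling and q are assumptions, as is completion by all 50 women. This is an inexpensive improvement to one of two blinding measures in a descriptive pilot, not an arithmetic error or a mismatch with the stated endpoint.

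**What to change.** In 10.5.2:

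- Keep the proportion correct and kappa for the demonstration bags, and report the proportion correct separately for the dummy and active arms. Mirror-image results in the two arms would suggest labelling by reference to the own bag; at q = 0.5 the arms look alike and this gives no signal.
- Add, as a descriptive measure from the two answers recorded under 7.5, the proportion of women who give the demonstration bag of their own true type the same label they gave their own bag, with an exact 95% interval set against 50%.
- State that a proportion correct near 50%, or kappa near zero, is not sufficient on its own, and that blinding is not judged on the added score alone. Describe the demonstration bags as indistinguishable only if neither score departs from chance in either direction.

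The cost is a few sentences and one cross-tabulation, with no new data. The downsides are one more statistic, informative mainly if women label by their own bag, and two chances of a spurious departure (at most 2 × 0.033 = 0.066 if the exact region above is applied to each). With 50 women the intervals are wide: 25 of 50 gives 36% to 64%.
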